1.0 Research Design

1.1 Purpose/Specific Aims

The overall purpose of the study is to test the effect of metformin on exercise intensity based training adaptations in adults with metabolic syndrome.

A. Objectives

Understand effect of metformin on training intensity mediated vascular versus metabolic insulin sensitivity in adults with metabolic syndrome for clinical health.

B. Hypotheses / Research Question(s)

The overarching hypothesis is that metformin may blunt adaptation following high intensity exercise by lowering/attenuating oxidative stress. Thus, compared with high intensity exercise plus metformin, low intensity exercise plus metformin will produce greater vascular insulin sensitivity and metabolic insulin sensitivity changes following 16 weeks of treatment. In addition, we anticipate that high intensity exercise based training alone will produce greater effects than low intensity exercise. Lastly, we hypothesize that these changes in metabolic and vascular insulin sensitivity will correlate with glycemic control and blood pressure changes.

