- This will take about 10 minutes and will occur before and after the 2 hour clamp technique during.

RANDOMIZATION and STUDY PROCEDURES

Subjects will be randomly assigned (like the flip of a coin) to 1 of 4 study treatment groups. Subjects have an equal chance of being assigned to any one of the groups. Neither the subject nor their doctor can choose which treatment they are assigned. Neither subject nor their doctor will know which study treatment they will get until the study is done. If the subjects doctor needs to know whether metformin or placebo pill is prescribed due to medical reasons that directly affects medical care of the subject, the people doing this study can find out.

PHASE 3: INTEREVENTION PERIOD (Visits 5-53)

Ambulatory Blood Pressure:

- This is used to look at blood pressure throughout the entire day and night for 24 hours.
- This measure occurs using a blood pressure cuff that is wrapped around the subjects arm with a holter monitor secured to their belt that contains a battery and recording device.
- Subjects are instructed to go about their normal activities throughout the day.
- During periods of inflation and deflation, we ask subjects to relax their arm.
- This test will occur before the first training session.
- At the same time, subjects will be given standardized meals to follow for the 24-hr collection period before and after the intervention.

The Ambulatory Blood Pressure will occur before the intervention period and within the last week of the intervention.

Prior to the intervention subjects will be randomized (like the flip of a coin) to receive 1 of 4 treatment options for 16 weeks – all of which expend a matched number of calories per week. *Note, due to COVID-19 if supervised exercise sessions need to vary for safety reasons, virtual sessions will be established within reason to maintain "supervised" sessions.*

- Low Intensity Exercise Training (LoEx) + Placebo
- High Intensity Exercise Training (HiEx) + Placebo
- LoEx + Metformin
- HiEx + Metformin

 $\underline{\textit{LoEx} + \textit{Placebo}}$: If subjects are randomly assigned to this group, subjects will participate in exercise training. Subjects will be asked to attend 3 regularly supervised and scheduled training sessions (e.g. M,

12/31/2499

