W, and F) with the exercise physiology staff at the Loree Gymnasium or IFNH on Cook-Douglas Campus. On the remaining 2 days a week (e.g. T and Thr) subjects will be instructed to exercise on their own for half the time that they do in the supervised training sessions. These days are designed to help subjects body recover. Overall, the training program will ask subjects to exercise 5 times per week. Subjects heart rate will be monitored continuously, and subjects will be asked to exercise at an intensity near 50-55% of theiir previously measured fitness level. The amount of time subjects exercise will vary based on capacity to burn 400 kcal on supervised days and 200 kcal on unsupervised days. During the first days of training we will measure breath samples during exercise to ensure proper exercise intensity and determine how many calories from sugar and fat subjects are burning for energy. Every 4 weeks subjects will have their body weight and waist circumference measured prior to a training session. In addition to this training program subjects will be provided a placebo. The Placebo is a harmless substance that looks like the study drug, but which should have no effect. Subjects will not be able to find out if they are on the placebo or metformin (i.e. the real drug) until the study is done. Pills will be provided to the subjects by the research team as prepared by Rutgers Pharmacy in the CRC on a weekly basis (i.e. [name], CRC Pharmacy). Unused pills should be returned to our research team. If the subject's doctor needs to know whether metformin or placebo pill is prescribed due to medical reasons that directly affect their medical care, the people doing this study can find out. At weeks 0, 8 and 16, accelerometers will be provided to characterize non-exercise physical activity. Breath samples during exercise will also occur at the end of training.

HiEx + Placebo: If subjects are randomly assigned to this group, subjects will participate in exercise training just as described above. However, here the exercise training intensity based on subjects heart rate will be near 85% of your previously measured fitness level. Exercise duration will vary in order to expend about 400 kcal per session on supervised days and 200 kcal on unsupervised days. In addition to this training program, subjects will be provided a placebo and accelerometer as described above.

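### The post-intervention 24-hour blood pressure falls in a training week and the baseline before any training, with no rule keeping a session out, so acute exercise effects that differ by intensity can enter the change.

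*Combined protocol and SAP*

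**What the plan says.** Under Ambulatory Blood Pressure in section 1.3 A, Phase 3, the baseline recording is placed before training ("This test will occur before the first training session"). The timing of the pair is then given as: "The Ambulatory Blood Pressure will occur before the intervention period and within the last week of the intervention". The schedule table in section 1.10 agrees. It marks 24-hour pressure in the pre-test OGTT column and the exercise-training column, and in no post-intervention testing column.

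During the recording, "Subjects are instructed to go about their normal activities throughout the day". Only meals are standardised: "subjects will be given standardized meals to follow for the 24-hr collection period before and after the intervention". That sentence puts the second recording after the intervention, which does not fit the last-week timing.

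On training, the LoEx paragraph says "Overall, the training program will ask subjects to exercise 5 times per week", with Monday, Wednesday and Friday supervised and Tuesday and Thursday unsupervised as the example. LoEx participants are to "exercise at an intensity near 50-55% of" their measured fitness. For HiEx, "the exercise training intensity based on subjects heart rate will be near 85% of your previously measured fitness level". Both programs aim at 400 kcal on supervised days and 200 kcal on unsupervised days.

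Blood pressure enters the third hypothesis in section 1.1 B: "these changes in metabolic and vascular insulin sensitivity will correlate with glycemic control and blood pressure changes".

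**The concern.** The two recordings are made under different conditions. No study session can fall in the baseline recording, but one can fall in or just before the post recording. The 24-hour change may then combine the lasting effect of 16 weeks of training with pressure during and after a single bout.

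Randomisation does not remove this, because the bout is part of the assigned arm. HiEx and LoEx sessions differ in intensity and, being matched on calories, probably in length. Any difference in acute response would therefore appear as a difference between training intensities. Two of the three hypotheses compare intensities, and the third relates blood-pressure change to the other outcomes. An acute component could mimic or mask an intensity effect on 24-hour pressure and could distort correlations that use it.

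**Working it through.** The plan states no effect size or power for 24-hour pressure, so there is no figure to reproduce. The check has three parts.

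**1. Does any rule keep a session out?**
- Phase 2 conditions (section 1.3 A) bar vigorous exercise for 72 hours before test days, but exempt exercise done within the training study.
- Phase 4 bars structured exercise for 24 hours before testing, but is written for Visits 54-56. The ambulatory recording belongs to Phase 3.
- The Phase 3 text on the recording restricts no exercise and gives no interval from the last session.
- Section 1.6 A plans a group-by-test repeated-measures ANOVA with no term for time since the last session.

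So no rule does.

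**2. How often could a session be caught?**
Inputs: five sessions in seven days (section 1.3 A). Assumptions: sessions at a fixed clock time, and recording start days spread evenly over the week.
- Each session lies in exactly one of the seven daily 24-hour windows, so the share containing a session is 5/7 = 71%. At baseline it is 0%.
- The share that contain a session or start within 24 hours after one is 6/7 = 86% if the two rest days are adjacent and 7/7 = 100% if they are not. With adjacent rest days, one start day in seven avoids both.
- If energy cost is proportional to intensity (assumption), a LoEx session lasts about 85/52.5 = 1.6 times as long as a HiEx session of equal calories.

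**3. What would this do to the contrasts?**
Let *f* be the share of post recordings containing a session, taken as equal in all arms. Let *s*H and *s*L be the acute shifts in the 24-hour mean under HiEx and LoEx.
- Within-arm change: shifted by *f* × *s*H or *f* × *s*L.
- HiEx minus LoEx: shifted by *f* × (*s*H − *s*L).
- Metformin minus placebo at one intensity: shift 0, unless metformin alters the acute response. Some noise is added.

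The documents do not give *s*H − *s*L. For an absolute value of 0 to 4 mmHg (assumption):
- All sessions weighted equally: 0 × 5/7 = 0, to 4 × 5/7 = 2.9 mmHg.
- 200 kcal sessions given half the effect of 400 kcal sessions: *f* becomes (3 + 2 × 0.5)/7 = 4/7 = 57%, so 0 to 4 × 4/7 = 2.3 mmHg.

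These figures count only windows that contain a session. Recordings that merely follow one are left out, since their shift could differ in size or sign.

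**The case against.** Several points on the other side carry weight.

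- **The recording day is not fixed.** A rest-day recording complies with the plan, so acute effects can enter but need not. A reader might infer that most post recordings do contain a session. That requires evenly spread start days, which no section states.
- **The last week may not be a full training week.** Visits 53, 54 and 55 are on consecutive days, and Phase 4 testing carries a 24-hour exercise limit. A calendar week that holds the clamp and OGTT on weekdays cannot hold five weekday training days. Five sessions fit if the last week means the seven days up to Visit 54. The intervention may also be lengthened or shortened by about a week.
- **One sentence places the recording after the intervention.** Read that way, no scheduled session would fall inside it. The explicit last-week sentence and the section 1.10 table make the other reading likelier, but the text conflicts.
- **The net acute difference could be nil.** LoEx sessions are less intense but probably longer, so a range for the bias must include zero.
- **The measure is not central.** Section 1.3 D makes basal FMD the primary outcome. The hypotheses refer to blood pressure generally, and the outcome list in section 1.6 B does not name ambulatory pressure. Resting pressure is taken at each testing visit, and post-intervention visits fall under the 24-hour limit.
- **Pressure on a typical training day may be the intended target.** That is legitimate, but the plan would then need to say so and fix the day type. At present the mix of training and rest days is left to scheduling.

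These points limit the size and certainty of the problem. They leave the unequal recording conditions in place.

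**Conclusion.** The concern stands as a possible bias that the plan does not prevent. It bears on the HiEx-LoEx contrast and the within-arm changes in 24-hour ambulatory pressure, and on correlations that use them. Under the stated assumptions (even start days, all sessions equal, acute intensity difference of 0 to 4 mmHg) the shift in the contrast is 0 to about 2.9 mmHg in either direction. It is smaller if half-dose sessions have a smaller effect.

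A reader might go further and conclude that the intensity contrast is certainly biased, or that the trial's blood-pressure results or main finding are compromised. The documents do not support that. They give no acute effect, no direction and no fixed recording day. The primary FMD outcome and resting pressure at test visits are outside this point. Metformin versus placebo at one intensity is balanced on session exposure, under the condition given in the working. The issue should be corrected because the remedy is cheap, but it is secondary.

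**What to change.** In section 1.3 A, Phase 3, under Ambulatory Blood Pressure:

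1. Schedule the post recording on a non-training day, starting at least 24 hours after the last session, in all four arms. Match the day type (weekday or weekend) to the participant's own baseline where possible. With the Monday-to-Friday example, a recording started on Saturday, 24 hours after Friday's session, qualifies.
2. Reconcile the meal sentence (after the intervention) with the timing sentence (last week of the intervention).
3. Log the time from the last session to the start of every recording.
4. For recordings already made, use session and heart-rate-monitor records to flag those that contain a session or start within 24 hours after one. Repeat the analysis without them as a sensitivity analysis.

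The cost is mainly scheduling, with no added assessment. The last week becomes tighter, and some monitors must be worn over a weekend. The section 1.10 table ties the baseline to the OGTT visit, so a matching weekend baseline may need a separate start. Section 4.3 describes a transferred study needing 45 of 80 people, so some baselines may already exist. For those participants the day-type match will be imperfect and should be reported.

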- In the morning of the pre and post study testing days in the CRC, an IV catheter will be inserted into a vein in either the forearm or hand. An IV is a small flexible tube that is inserted into a vein guided by a needle. Once the tube is in place the needle is removed and replaced with cap that allows blood to be withdrawn or fluids or medications to be given
- The IV catheter will be in the subjects arm for the remainder of each visit (about 4 hours) and removed before they leave the Clinical Research Center.
- Blood we take will be tested to measure sugars, lipids, and hormones that estimate blood glucose and vessel health.
 - o Visits 3 and 55: about 8 tablespoons of blood (40 cc) will be drawn per visit.
 - o Visits 4 and 54: about 18 tablespoons of blood (90cc) will be drawn per visit.
 - O Visit 58: about 10 tablespoons of blood (50 cc) will be drawn.
 - Additional blood (about 1 tablespoon or 15 cc) may be drawn to verify results of the screening visit at the discretion of the investigator.
- When the blood draws are completed subjects will be fed lunch and discharged to go home.
- The amount of blood collected pre and post study is approximately the same as donating a pint of blood. As a result, subjects are advised not to donate blood while participating in this study.
- Visit 3 and visit 4 tests will be performed about 24 hours or more apart.

Glucose Metabolism test (i.e. blood sugar): Visit 3 or 4, 54 or 55, and 58

Oral Glucose Tolerance Test (OGTT) (approximately 4 hours)

• Subjects will report to the CRC fasted for about 10 hours and participate in an OGTT, and we will put an intravenous catheters (IV) into a vein in the arm and obtain baseline blood samples.

12/31/2499

- The OGTT is used to help determine how quickly sugar is removed from the blood. After the blood sample is taken for the fasting blood sugar test, subjects will drink a sugary solution. Five more blood draws will be taken at 30, 60, 90, 120, and 180 minutes after subjects receive the drink. This procedure will also include a measure of blood flow at 0, 60 and 120 called flow-mediated dilation (see below).
- Participants will complete items on the NIH toolbox for related to working/episodic memory, executive function and attention. The NIH toolbox is an iPad application that consists of cognitive, emotional, motor and sensory function assessments. This will take about 20 minutes and will be completed prior to consuming the 75g and after the 120 minute mark.

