Euglycemic-Hyperinsulinemic Clamp (approximately 6 hours)

- Subjects will arrive at the CRC fasted for about 10 hours, and we will put two intravenous catheters (IV) into two vein in the subjects arm and obtain baseline blood samples.
- During this visit, we will perform the 2-hour euglycemic-hyperinsulinemic clamp or "clamp" study. This test is the gold standard for measuring sensitivity to insulin.
- Since the clamp study can be significantly enhanced by the use of glucose tracers, we will inject a glucose labeled with tracer (~2 drops) called dideuterated glucose (Dideuterated glucose is non-radioactive). The tracer contains a very small amount of heavy hydrogen (²H₂), which makes the glucose more identifiable. A small percentage of heavy hydrogen is naturally present in your body (0.015%). What we do is add to this natural pool and measure its concentration in the blood. This allows us to determine how insulin is controlling your rate of liver glucose production vs. skeletal muscle glucose uptake. The infusion of dideuterated glucose through the IV is continued during an entire 4-hour period (2 hour before the clamp and 2 hour for the clamp, i.e. about 4 hour total).
- Subjects will not eat, drink, or take any medications/vitamins on the morning of the test.
- Subjects will be given a meal once the "clamp" study is complete.
- Insulin will be infused at a constant rate to maintain the blood concentration at approximately 100 μU/ml. Subjects blood sugar concentration will be measured every 5 minutes and infused at a variable rate to maintain a normal blood sugar level (90 mg/dl). Blood draws for insulin will occur every 30 minutes up to 90 minutes, and then every 10 minutes until the end of the clamp.
- Subjects will also have a see-through canopy (cover) over their head before and at the end of the clamp. This procedure uses the same machine used during exercise in screening visit 2, part B above. This device allows us to measure how much sugar and fat you are using to create energy. Also, by measuring and analyzing the oxygen and carbon dioxide levels in the subjects breath it is possible to estimate if subjects are storing glucose as glycogen.

Urine Collection:

• Subjects will be provided with a plastic container and asked to collect one urine void on visit 3 and 4. The amount and time of subjects urine collection will be recorded and analyzed for nitrogen, protein and metabolites.

Blood flow to be done at Visit 3 and/or 4, 54 and 58:

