Blood pressure:

 Subjects blood pressure will be taken at the beginning of each testing visit. This test takes about 5 minutes.

Large artery flow-mediated dilation (FMD):

• This test allows us to measure the blood flow through the subjects arteries.

12/31/2499

- This procedure uses an ultrasound device to measure blood flow in an artery in the subjects upper arm and leg. Ultrasound is a diagnostic procedure that creates a picture image using sound waves. Unlike X-rays, ultrasound does not involve radiation.
- Just prior to the test subjects will be asked to lie down on a bed quietly for 20 minutes. During this time, subjects will have blood pressure taken, and subjects will be connected to an electrocardiogram (ECG) that will monitor your heart rate. After the 20 minutes have passed, an ultrasound probe will be lightly pressed against the inside of the subjects upper arm and leg.
- Next we will place a blood pressure cuff on the subjects forearm only and pump it up tightly. This
 portion of the test may cause some discomfort in their forearm and fingers (such as pain, tingling,
 and numbness).
- We will keep the cuff inflated for 5 minutes, take images, then release it, and measure the increase in blood flow in one of the arteries in your upper arm using the ultrasound probe.
- This procedure takes about 15 minutes. We will perform this procedure just before the glucose beverage during the OGTT, and then again at 1, and 2 hours after you drink the glucose beverage.
 For the clamp test, we will perform blood flow measures once at the beginning and once at the end.

Common carotid artery intima-media thickness (CCA-IMT)

- This test allows us to measure the level of blood vessel thickness in the artery.
- This procedure uses an ultrasound device, similar to FMD above, to measure degree of vascular tissue thickness between the inner 2 layers of the vessel wall in an artery of the upper neck. Ultrasound is a procedure that creates a picture image using sound waves. Unlike X-rays, ultrasound does not involve radiation.
- This procedure takes about 15-20 minutes.
- Prior to the test the subject will be asked to lie down on a bed quietly for about 15 minutes. During
 this time, blood pressure will be taken, and the subject will be connected to an electrocardiogram
 (ECG) that will monitor heart rate. Then an ultrasound probe will be lightly pressed against the
 subjects neck. Images will be taken for about 5 minutes.

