LoEx + Metformin: If subjects are assigned to this group, subjects will participate in the same LoEx exercise program as outlined above. But here you will be provided metformin. Metformin is a common medication routinely used to treat high blood sugar and has secondary effects on vascular health. Subjects will not be able to find out if they are on metformin until the study is done. If the subjects doctor needs to know whether metformin or placebo pill is prescribed due to medical reasons that directly affect the subjects medical treatment, the people doing this study can find out.

HiEx + Metformin: If subjects are assigned to this group, subjects will participate in the same HiEx exercise program and receive metformin as outlined above.

PHASE 4: POST INTERVENTION TESTING (Visits 54-56)

After the 16 week intervention subjects will be asked to undergo the same series of testing that they completed in phase 2. Subjects cannot drink alcohol or take medications/supplements 24 hours prior to testing unless approved by the study team. In addition, subjects cannot eat or drink foods that contain caffeine 24 hours prior to testing. We also ask that subjects refrain from any structured exercise for 24 hours prior to testing and limit exercise to your normal everyday activities. All study testing visits highlighted above in Visits 2, 3 and 4 (Body Composition, Fitness, AI, PWV, OGTT, etc.) will be repeated (except physical screening and resting ECG). The order of the tests post-intervention will be:

- 1. Clamp Study (Visit 54)
- 2. OGTT (Visit 55)
- 3. Body Composition and Fitness (Visit 56)

Visits 53, 54 and 55 will be on consecutive days (i.e. 1 day apart).

*Intervention (medication and exercise) may be extended or shortened by approximately one week if scheduling requires to complete visits 54 and 55 of post-intervention testing.

PHASE 5: Unsupervised Exercise Follow-up (Visit 57-58)

12/31/2499

After the post-intervention testing, subjects will be asked to exercise on their own (e.g. purchase a gym membership, etc.) while wearing the polar activity tracker watch and heart rate strap. We ask that subjects exercise at the same intensity that you have been exercising with us during the intervention. We will check in by phone within week 2 to see if they are exercising, or if there are any complications.

Visit 57 approximately 30 min

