During week 4, subjects will come to Loree Gymnasium/IFNH to check in with the study team. At this visit subjects will receive an accelerometer to wear for 7 days, 3-day diet logs to fill out, and will have waist circumference and weight measured. We will provide subjects a pre-stamped envelope to return the diet log and accelerometer within 7 days.

Visit 58 (about week 8-10) approximately 6 hours

We will provide an accelerometer and diet logs to complete an approximate week prior to the subjects final testing. You will return these items at your testing visit. At this visit, you will also turn in your HR strap.

- A. Oral Glucose Tolerance Test (OGTT) (approximately 4 hours):
 - Subjects will report to the CRC fasted for about 10 hours and participate in an OGTT.
 - Subjects will be provided standardized meals and snacks the day prior to and during all blood test visits (listed below) consisting of 55% carbohydrate, 30% fat, 15% protein.
 - Subjects must not drink alcoholic/ caffeinated drinks for at least 24 hours before the study testing visit begins.
 - Subjects must not use allergy, prescription or pain-related medicines (over-the-counter or prescription) or antioxidant dietary supplements for at least 24 hours prior to each testing visit. Prescription meds may be taken after testing.
 - Subjects must not perform any vigorous exercise for 72 hours prior to each test day. In particular, subjects are to complete you typical "supervised" exercise session 48 hours prior to this test.
 - The tests must be performed in the fasted state, so subjects may not eat or drink anything (except water) after about 9:00 pm the night before.
 - About 10 tablespoons of blood is taken during this test through an intravenous catheter.
 - The OGTT is used to help determine how quickly sugar is removed from the blood. After the blood sample is taken for the fasting blood sugar test, you will drink a sugary solution. Five more blood draws will be taken at 30, 60, 90, 120, and 180 minutes after you receive the drink. This procedure will also include measurements of blood pressure, heart rate, flow mediated dilation, augmentation index, pulse wave velocity, common carotid artery intima-media thickness and resting metabolic rate as described above in Visits 3 and/or 4 (excluding CEU).
 - Sleep history, physical activity enjoyment, and vetran rand questionnaires will be given during this visit.

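### The plan contradicts itself on whether FMD is taken at the post-intervention OGTT (Visit 55) and on exercise before Visit 58; follow-up FMD is affected, the primary contrast is not

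*Combined protocol and SAP*

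**What the plan says.** All of this is in section 1.3 A of the combined protocol unless stated.

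**FMD at Visit 55**
- The glucose-test heading gives the visits: "Glucose Metabolism test (i.e. blood sugar): Visit 3 or 4, 54 or 55, and 58". The OGTT description beneath it adds: "This procedure will also include a measure of blood flow at 0, 60 and 120 called flow-mediated dilation".
- The FMD description agrees: "We will perform this procedure just before the glucose beverage during the OGTT", with further readings at 1 and 2 hours.
- Phase 4 repeats the Phase 2 tests, fixes the clamp at Visit 54 and the OGTT at Visit 55, and puts Visits 53, 54 and 55 on consecutive days.
- The blood-flow heading, under which FMD sits, reads: "Blood flow to be done at Visit 3 and/or 4, 54 and 58". Visit 55 is absent.
- In the section 1.10 timetable, the FMD row read by column position is marked at both pre-tests, Visit 54 and Visit 58, and is blank at Visits 55-56. The table is broken in the text available to me, so I give it less weight than the prose list.

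**Exercise before testing**
- Phase 4: participants should "refrain from any structured exercise for 24 hours prior to testing".
- Phase 5, Visit 58, where FMD is repeated within the OGTT: "Subjects must not perform any vigorous exercise for 72 hours prior to each test day". The next sentence asks for the typical session 48 hours before the test.
- Phase 5, training intensity: "We ask that subjects exercise at the same intensity that you have been exercising with us during the intervention". That is near 85% of measured fitness in HiEx and 50-55% in LoEx.
- Phase 2 has its own 72-hour rule, but exempts exercise done as part of the study. The Visit 58 version has no exemption.

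Section 1.3 D makes the primary outcome the change in basal FMD before the clamp, so its post-intervention value comes from Visit 54. Section 1.6 does not say what Visit 58 FMD is compared with.

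**The concern.** Visit 58 is the only FMD measurement after supervised training ends, so it is what shows whether a gain lasts. The natural comparator is the 0-minute FMD of the post-intervention OGTT, which is the same type of test day. If staff work from the visit list or the timetable, that value is never taken and cannot be recovered at analysis. What remains is a clamp-day value with a different minimum interval since exercise.

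The Visit 58 exercise rules raise a separate problem. Where two instructions conflict for one intensity only, HiEx participants may rest for 72 hours while LoEx participants train at 48. Time since the last bout would then vary with the factor under study. The plan sets limits on recent exercise before every test, so it treats the interval as something to control.

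**Working it through.** The plan gives no figure of its own on this point. The check is mainly a comparison of the rules.

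**1. FMD time points on OGTT days**

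| Source | Baseline | Visit 55 | Visit 58 | Count |
|---|---|---|---|---|
| OGTT and FMD descriptions, with Phase 4 | yes | yes | yes | 3 of 3 |
| Blood-flow visit list | one or both pre-test visits | no | yes | at most 2 of 3 |
| Timetable (by column position) | yes | no | yes | 2 of 3 |

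**2. Hours from the last session to FMD**

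Phase 2 sets arrival at 06:30-09:00. Suppose Visit 53 is a session ending no earlier than 06:00 (my assumption) and the 24-hour rule is kept.
- To Visit 54 arrival: minimum 24 h by rule; maximum 24 + (9 − 6) = 27 h.
- To Visit 55 arrival: minimum 48 + (6.5 − 9) = 45.5 h; maximum 48 + (9 − 6) = 51 h.
- To Visit 58: 48 h by the second Visit 58 sentence, or at least 72 h for a HiEx participant who follows the first.

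Visit 53 need not be a session. Visits 5-53 are 53 − 5 + 1 = 49 visits, while section 1.3 C counts 48 training visits. If the last session falls 48 h before Visit 54, the gaps are about 48 h at Visit 54 and 72 h at Visit 55, and it is then Visit 54 that matches Visit 58 on interval.

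**3. Visit 58 rules by arm**

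A session at 48 h lies inside a 72-hour ban. HiEx (near 85%) breaks the ban if that intensity is vigorous, a term the plan does not define. LoEx (50-55%) need not.

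**4. Illustration only: what a transient bout effect would do**

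Assume a HiEx bout effect of d FMD points present at 24 h and gone by 48 h, with no true change from Visit 54 to Visit 58. Take a paired t-test in one arm of 15 at two-sided 0.05, with SE = SD/√15 and power from the noncentral t on 14 df. SD 3.4 is section 1.5's value for pre-to-post change; using it for this difference, and SDs of 2 and 4.8, are my assumptions.

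| SD | SE | d = 0.5 | d = 1 | d = 2 |
|---|---|---|---|---|
| 2 | 0.516 | 15% | 44% | 95% |
| 3.4 | 0.878 | 8% | 19% | 56% |
| 4.8 | 1.239 | 7% | 12% | 32% |

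Each entry is the chance of a significant change, against a nominal 5%.

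**5. Could the trial detect such an effect itself?**

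Compare the Visit 54 minus Visit 55 basal FMD difference between HiEx and LoEx, 30 v 30: SE = SD × √(2/30), df 58, t = 2.002. At SD 3.4 the SE is 0.878 and the 95% half-width is 1.76 points, or 1.76/4.2 = 42% of the planned detectable difference. Half-widths at SD 2 and 4.8 are 1.03 and 2.48 (25% and 59%). Power at SD 3.4 is about 9%, 20% and 61% for 0.5, 1 and 2 points.

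**The case against.** The best case against the point is that both conflicts are drafting slips.

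- **Visit 55.** Three places put FMD there. The blood-flow heading cannot be exhaustive, because blood pressure is listed under it yet is taken at every testing visit. The timetable is unreliable: the row that includes contrast-enhanced ultrasound is marked at Visit 58, where the text excludes that test. I accept that Visit 55 FMD was probably intended. The list is still plain prose that names visits, and staff who follow it would omit the reading.
- **Visit 58.** The 48-hour sentence is specific and underlined, and may be meant to qualify the 72-hour one. It does not say so, and the exemption that would settle it appears only in Phase 2.
- **Consequence.** No section names a Visit 54-to-58 FMD contrast, and the percentages above rest on an assumed effect. Both statements are correct.
- **Remedy.** Visit 55 is not a perfect match for Visit 58. It falls the day after a clamp, and its interval is near 48 hours only if Visit 53 is a session. This stands, and is why the hours should be recorded.

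A reader might infer that the primary result is compromised. The documents do not support that: Visit 54 FMD is collected under either version, with the same 24-hour rule in all four arms. A reader might also infer that a fall from Visit 54 to Visit 58 would be a last-bout artefact. The documents do not show that such an effect exists, its size or its direction.

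**Conclusion.** The point holds as two internal contradictions with consequences for secondary and follow-up FMD only.

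1. Depending on which text is followed, OGTT-day FMD has all 3 time points or at most 2. In the latter case, Visit 58 has only a clamp-day post-intervention comparator, taken under a 24-hour rule.
2. The Visit 58 exercise rules cannot both be met in HiEx, provided training near 85% of fitness is vigorous. They can both be met in LoEx, so the last-bout interval could be at least 72 hours in HiEx and 48 in LoEx.

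Neither conclusion needs a bout effect to exist. The false-positive percentages show what such an effect could do and are not an estimate of bias in this trial. The correction is worth making because it decides what is measured and what participants are told, and costs little.

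**What to change.** - **Visit list and timetable.** Add Visit 55 to the FMD visits in the section 1.3 A blood-flow heading and to the FMD row of section 1.10.
- **Comparator.** State in section 1.6 that follow-up FMD is compared on OGTT days: baseline, Visit 55 and Visit 58. Keep clamp-day basal FMD as the primary outcome.
- **Interval.** Record hours since the last exercise session at every FMD visit. Leave the consecutive-day schedule of Visits 53-55 as it is.
- **Visit 58 rule.** Carry the Phase 2 exemption for study training into the Visit 58 72-hour sentence, so that all four arms do their usual session 48 hours beforehand.
- **Optional.** Report the Visit 54 minus Visit 55 basal difference, HiEx against LoEx, with a 95% interval. Test-day effects should be similar across arms, so interpret only the between-intensity difference. It can rule out a large carry-over but not a small one.

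**Cost.** If FMD at Visit 55 was always intended, this is wording, one recorded item and a stated comparison. If not, it adds about 15 minutes for the 0-minute reading, or 3 × 15 = 45 minutes for the full series, at a visit already scheduled. No extra visits or participants are needed.
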